**b. Secondary outcome variables.**

1. Metabolomics – We will store plasma before and after the study intervention to assess the effect of the study medication on fasting bile acid levels. This will enable us to determine whether the study drug raised the levels of bile acids that were deficient in people with MS. Targeted metabolomics analyses will be performed through Metabolon Inc.
2. Gut microbiota – The composition of the gut microbiota is closely related to bile acid metabolism, and alterations in bile acid receptor (FXR) signaling can significantly affect composition of the gut microbiota[37],[38]. We will collect first morning stool specimens prior to and following study treatment to determine the effect of bile acid supplementation on the gut microbiota in people with MS.
3. Immunophenotyping – We will store PBMCs from before and after the study intervention to assess the effect of TUDCA supplementation on the peripheral immune system. Our laboratory has expertise in immunophenotyping people with MS and assessing the effect of

therapeutic interventions on peripheral immune cell function. These assays will be performed at the end of the study.

4. Other outcomes – We will also collect information regarding quality of life using the MSQOL-54 instrument[39] administered at the visits noted in the table above. We will also measure lipid profile and hemoglobin A1c at baseline and end-of-study, since bile acid metabolism is linked to obesity and metabolic syndrome.

Assessment of important covariates: We will collect demographic information including age, gender, cigarette smoking, waist circumference, and BMI which can affect circulating bile acid levels. Another critical factor that can affect bile acid metabolism and the gut microbiota is diet. Since TUDCA could potentially lead to GI side effects, this may result in a change in diet. To monitor changes in diet we will perform the Block Food frequency questionnaire before and after the study intervention. Since antibiotics and probiotics can lead to changes in the gut microbiome and could also affect bile acid metabolism, we will collect detailed information on the use of both these covariates so they can be adjusted for in our final analyses.

**c. Statistical plan including sample size justification and interim data analysis.**

Safety data will be analyzed as they are captured in real time. Assessments will focus on AEs (including study treatment tolerability assessments, laboratory evaluations, vital signs and physical examination). The incidence rate of AEs will be recorded by system organ class, severity and by relationship to study treatment. Tolerability analysis will be based on the number (%) of participants who failed to complete the study due to adverse events. Lab values for each parameter will be summarized by shift tables. For quantitative parameters, we will present summary statistics for actual values and change from baseline. We will compare changes over the 16-week treatment period between the groups using mixed effects regression analyses to account for repeated measures using random subject-specific intercepts and slopes.

Metabolomics data will be analyzed at the end of the study following quantitation of the 15 bile acids included in our panel. Summary statistics will be used to characterize these outcomes. We will then assess normality of these measures and perform appropriate univariate testing to determine which bile acids are significantly altered by TUDCA supplementation. A mixed effects longitudinal model will also be used to test which bile acids are altered between visits across the two groups. Models will also adjust for important covariates including BMI, age, gender and measures derived from the food frequency questionnaire.

Gut microbiota data, *a priori* analyses will assess changes in relative abundances of different gut bacteria as well as microbial genes that encode bile acid metabolizing enzymes (identified from the literature and NCBI Gene database) which occur as a result of TUDCA treatment. Exploratory analysis will assess the effects of TUDCA on the metagenome using a combination of pathway and set-based approaches previously applied in metagenomics analysis of MS and other diseases to identify other biologically relevant changes[41]–[43].

Immunophenotyping data, we will summarize data using summary statistics (mean and standard deviation), before and after study treatment. We will utilize paired *t* tests to compare proportions of various immune cell sub-populations at different time points. For both sets of data we will utilize mixed-effects regression models to assess the change in bacterial taxa/ metagenomics pathways/ immune cell subsets over time, and determine their relationship to changes in bile acid concentrations with TUDCA supplementation.

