**Trials of bile acid supplementation have been conducted in other neurodegenerative conditions and have shown good safety profiles and CNS penetration.** A recent trial of TUDCA in 34 ALS patients randomized to either TUDCA 1gm twice daily or placebo for 54 weeks revealed a higher rate of response (defined as slowing in the slope of decline on a standardized rating scale) in the TUDCA arm[25]. TUDCA was well tolerated and there were no serious adverse effects in this trial. Two patients in the TUDCA arm of the trial had mild diarrhea and none of the patients had any changes in safety laboratory parameters that were monitored. A previous trial of UDCA in ALS employed a cross-over design and utilized 3.5 gm/day of UDCA for 3 months[26]. This trial found a reduction in the slope of decline in one of the three outcomes utilized. There was a high attrition rate related to GI adverse effects of UDCA. Another trial of UDCA supplementation in ALS revealed a dose-dependent increase in CSF UDCA concentrations, demonstrating good CNS penetration[27]. The European Medicines Agency (EMA) recently accorded orphan drug status to TUDCA for the treatment of ALS in Europe. Trials are also ongoing in Huntington's disease and PD (NCT02967250, NCT00514774).

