**4. Study Procedures**

**a. Study design, including the sequence and timing of study procedures**

This will be a randomized, double-blind, placebo controlled trial of TUDCA 1gm twice daily versus placebo in patients with progressive MS who satisfy the inclusion and exclusion criteria. A pictorial representation of the trial design is shown here.

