**6. Drugs/ Substances/ Devices**

**a. The rationale for choosing the drug and dose or for choosing the device to be used.**

Tauroursodeoxycholic acid (TUDCA) is a hydrophilic bile acid that is normally produced endogenously in humans in the liver, by conjugation of taurine to UDCA. It is used in Europe to treat cholestatic liver disease and gallstones. TUDCA has been used in trials for liver cirrhosis, primary biliary cirrhosis, transthyretin related amyloidosis, cholesterol gallstones, diabetes, and ALS[30]–[33], with a good safety profile. Diarrhea was the most common side effect noted in these studies, which utilized varied doses of TUDCA.

As noted in the background section, we chose TUDCA as an intervention since it has been previously demonstrated to be safe and have several beneficial effects (on ER stress, mitochondrial dysfunction, immunological effects and neuroprotection) that could potentially lead to benefits in patients with MS. Additionally since TUDCA can change the circulating bile acid pool this could potentially help correct this metabolic abnormality that we have identified in our preliminary studies.

We will obtain TUDCA from Bruschetini S.r.l (Genoa, Italy). This medication is manufactured as 250 mg capsules and hence participants will take 4 capsules two times a day of either TUDCA or placebo. The study medication will be provided through the Johns Hopkins investigational drug services and will appear identical to maintain blinding. TUDCA is approved in Italy for the treatment of cholestasis and gallstones. It was recently accorded orphan drug status by the European Medicines Agency for the treatment of Amyotrophic lateral sclerosis.

Dose: We chose a dose of 1 gm BID based on the trial of TUDCA in ALS that was recently completed across three centers in Italy[25]. Participants in this trial had no significant adverse

events on TUDCA, and there appeared to be some evidence for a benefit in this early phase study. This dose is higher than the dose utilized in treatment of cholestatic disease and is close to the 30 mg/kg dose utilized in a trial of UDCA in ALS that was well tolerated and showed no significant difference in serum and CSF concentrations compared to a higher dose of 50 mg/kg[27],[30].

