## 7. Study Statistics

**a. Primary outcome variable.**

The primary outcome of this study is the safety and tolerability of TUDCA supplementation. This will be based on number of adverse events occurring in the two treatment groups and the rate of drop-out in each study arm. This data will be documented at each study visit.

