## 8. Risks

### a. Medical risks, listing all procedures, their major and minor risks and expected frequency.

TUDCA treatment: In previous studies of TUDCA and UDCA – adverse effects include – mainly GI related effects – diarrhea, constipation, gas, nausea, vomiting, abdominal pain and anorexia, other adverse effects which are less frequent (< 1% each) include – headache, rash and pruritus [25],[27],[30].

While no serious adverse effects have been note in previous studies, several of the described AEs could lead to issues with tolerability in MS patients especially those with bowel function abnormalities.

In a recent trial of TUDCA 1 gm twice daily in patients with Amyotrophic lateral sclerosis there were no serious adverse effects.

Venipuncture: The potential risks include discomfort, bleeding or bruising at site of blood draw, and in rare cases fainting or infection.

Clinical examination (including EDSS, MSFC): There are no significant risks of this procedure.

Stool specimen collection: There are no significant risks of this procedure.

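### No measurement of capsule intake is described, so a participant who cuts or stops the capsules because of adverse effects but attends week 16 does not count towards intolerance

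*Combined protocol and SAP*

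**What the plan says.** Section 4a describes a "randomized, double-blind, placebo controlled trial of TUDCA 1gm twice daily versus placebo" and section 4b gives a duration of 16 weeks. Section 6a gives the capsule strength ("This medication is manufactured as 250 mg capsules") and the regimen: "participants will take 4 capsules two times a day of either TUDCA or placebo".

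Section 7a defines the primary outcome, safety and tolerability: "This will be based on number of adverse events occurring in the two treatment groups and the rate of drop-out in each study arm". Section 7c narrows the tolerability part: "Tolerability analysis will be based on the number (%) of participants who failed to complete the study due to adverse events". It also mentions tolerability assessments of study treatment among the adverse event assessments, without defining them.

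The visit lists and schedule table in section 4a cover adverse events, concomitant medication, examinations, laboratory tests, questionnaires, and blood and stool samples. Section 8a acknowledges of the expected adverse effects that "several of the described AEs could lead to issues with tolerability in MS patients especially those with bowel function abnormalities". Section 7b plans a food frequency questionnaire because gastrointestinal effects might change diet; it has no counterpart for capsule intake.

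**The concern.** Whether people tolerate a regimen depends partly on whether they go on taking it. Both completion measures in the plan record whether the participant leaves the study, not whether the assigned dose was taken. With capsules taken at home and mainly gastrointestinal effects expected, cutting back while remaining in the study is a plausible response, and the stated rule cannot see it.

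At stake is the claim the trial is built to support, that 1 g twice daily is tolerable. Applied exactly as written, the rule can understate intolerance of that dose. Intake that is not recorded during the trial cannot be reliably reconstructed afterwards.

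**Working it through.** **1. The plan's dose figures.** The inputs are 250 mg capsules, four per dose and two doses a day (section 6a), for 16 weeks (section 4b).
- Per dose: 4 × 250 mg = 1,000 mg, which reproduces the 1 g dose in section 4a.
- Per day: 4 × 2 = 8 capsules, or 2 g.
- Full course: 8 × 7 × 16 = 896 capsules per participant.

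**2. Search for an intake measure.** The nearest items, place by place:

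| Place | Nearest item | Measures intake? |
|---|---|---|
| 4a, visit lists | Concomitant medication update | No |
| 4a, schedule table | Medication review, including antibiotics and probiotics | No capsule count or return stated |
| 4a, study personnel | Coordinator phone check-in | Content and timing not given |
| 4f | Removal of those who cannot meet study requirements | No intake threshold, no means of detection |
| 6a | Supply through the investigational drug service | No return or accountability step stated |
| 7b | Plasma bile acids before and after treatment | Secondary outcome, not designated an adherence check |
| 7c | Tolerability assessments | Undefined |
| 7d | Treatment stopped if the drug is not tolerated | No rule for recording or analysing partial dosing |

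**3. What the rule does with a completer who cuts the dose.** Section 7c counts people who did not complete the study because of adverse events. Section 7a counts drop-outs. A participant who takes part of the dose, or none, and attends week 16 has not dropped out, so the contribution to both numerators is zero. Someone whose treatment is stopped under section 7d but who stays for the final visit is ambiguous, because the analysis refers to completing the study and not to completing treatment.

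**4. Illustration of size.** Section 7c plans 30 per arm with 10% drop-out (27 / 0.90 = 30). Assume that all 3 drop-outs in the TUDCA arm (10% of 30) are due to adverse events, and that k further completers cut their intake because of adverse effects. The values of k are assumptions; the documents give no rate.
- Planned measure: 3/30 = 10% for every k.
- Share not tolerating the assigned dose: (3 + k)/30.

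| k | Planned measure (exact 95% CI) | Counting dose-cutters (exact 95% CI) |
|---|---|---|
| 0 | 10% (2.1 to 26.5%) | 10% (2.1 to 26.5%) |
| 3 | 10% (2.1 to 26.5%) | 20% (7.7 to 38.6%) |
| 6 | 10% (2.1 to 26.5%) | 30% (14.7 to 49.4%) |
| 9 | 10% (2.1 to 26.5%) | 40% (22.7 to 59.4%) |

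The planned measure does not move with k. At k = 9 the point estimate of 40% lies outside the interval the plan would report.

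**The case against.** **Adverse events are the other half of the primary outcome.** A participant with diarrhoea who cuts capsules should still appear as a gastrointestinal event, tabulated by severity and relationship to treatment. This stands. A reader might infer that leaving the study is the plan's only tolerability measure, and the documents do not support that. What is lost is whether the assigned dose was taken. Nor does it follow that the adverse event rate is diluted: in this scenario the event comes before the dose cut and is reportable.

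**Exposure is partly visible.** Plasma bile acids are measured before and after treatment, and section 7c plans to relate microbiome and immune changes to changes in bile acid concentrations. It would therefore go too far to infer that a null result on either aim could not be told apart from non-intake, since gross non-intake might show. Two limits remain. The 15 acids in the panel are not listed, so it is not known that TUDCA is among them. Samples before and after treatment also do not show intake between visits or the reason for missed doses. Some loss of sensitivity is possible. Suppose the effect is proportional to intake and 20% of the arm take half the dose. The mean effect is then multiplied by 1 − 0.2 × 0.5 = 0.90, and power at 27 per arm falls from 85% to Φ(0.90 × (1.960 + 1.036) − 1.960) = Φ(0.737), about 77%.

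**The background evidence is mild.** Section 3 says of one earlier trial: "There was a high attrition rate related to GI adverse effects of UDCA". That was 3.5 g/day of a different bile acid, and those participants left, which a completion measure would capture. The same section reports that TUDCA at the present dose was well tolerated in a 34-patient ALS trial, with mild diarrhoea in two treated patients. This stands too: the documents do not show that dose-cutting will be common.

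**Other procedures may exist.** The phone check-in or the drug service may in practice pick up unused capsules. The protocol does not say so, and no analysis would use the information.

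**Conclusion.** The concern holds as a gap in measurement and analysis. The protocol describes no record of study-capsule intake, and its two completion measures count only leaving the study. A participant who reduces or stops the capsules because of adverse effects and attends week 16 is therefore not counted as intolerant by either.

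The size is unknown. The 20%, 30% and 40% figures rest on assumed numbers of such completers and on the assumption that the whole 10% drop-out is due to adverse events. They show how far the planned percentage could fall short, not how far it will. The trial remains valid and its adverse event data remain informative. The conclusion at risk is specifically that 1 g twice daily is tolerable as assigned. The change should be made before data collection is complete.

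**What to change.** - **Visits (section 4a).** Add return and count of study capsules to the week 8 and week 16 lists and the schedule table, with the reason for missed capsules (adverse event or other). Record the date of first dose, which the three-visit option leaves to the participant's home, so that the number of capsules assigned can be calculated.
- **Analysis (section 7c).** Report by arm the number (%) with adverse-event-related dose reduction, interruption or treatment discontinuation, alongside adverse-event-related study non-completion. Summarise the share of assigned capsules taken. A preset threshold such as 80% is optional.
- **Supporting check.** If TUDCA is in the 15-acid panel, state that plasma levels will be summarised by arm as an exposure check.

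These changes use existing visits and alter no dose or clinical rule. The cost is a short case report form item and some coordinator time. The tolerability figure may also look less favourable than the completion rate alone.

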#### 2. Objectives

##### Primary Objectives

**Aim 1. Establish the safety and tolerability of bile acid supplementation and determine whether this intervention leads to normalization of the bile acid profile in people with progressive MS with abnormal bile acid metabolism**

*Hypothesis: Bile acid supplementation is safe and tolerable and will help normalize the bile acid profile in people with MS.*

**Method:** In a randomized, double-blind, placebo-controlled, phase 1/2 study of bile acid supplementation in people with progressive MS with abnormal bile acid metabolism, we will establish the safety and tolerability of this intervention and evaluate its effects on bile acid profiles as determined by targeted metabolomics.

**Aim 2. Assess the effects of bile acid supplementation on the gut microbiota and the peripheral immune system in people with MS**

*Hypothesis: Bile acid supplementation leads to alterations in the gut microbiota and peripheral immune system in people with MS.*

[figure not shown]
**Method:** We will determine the change in gut microbiota composition following bile acid supplementation and determine changes in peripheral immune cell function in participants enrolled in the phase 1/2 trial of bile acid supplementation mentioned in Aim 1.

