#### Sample size justification

Since this is primarily a safety study we based our sample size on the ability to detect changes in our secondary outcomes, especially metabolomics. Previous studies of supplementation of UDCA and TUDCA have resulted in alterations in the total serum bile acid levels (2-8 fold change) and the composition of the bile acid pool. Based on our preliminary data, to detect a 50 - 70% change in levels of an individual bile acid, with a power of 85% and two-tailed alpha of 0.05 the required sample size would be between 14 – 27 in each arm. Accounting for a 10% drop-out rate, we will aim to recruit 30 participants in each arm of the trial. We have previously noted significant alterations in metabolic profiles in MS patients treated with vitamin D and dimethyl fumarate in studies utilizing between 18-24 patients (as shown in preliminary data).

From a safety stand-point, a sample size of 30 would enable us to conclude with 80% confidence that the rate of occurrence of serious adverse events with TUDCA treatment was less than 5% if none of the patients experienced a serious adverse event during the study[40].

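### For AE incidence and drop-out, the plan's primary outcome is only per-arm counts and percentages, with no TUDCA-minus-placebo difference or interval behind Aim 1's claim to establish safety and tolerability

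*Combined protocol and SAP*

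**What the plan says.** Section 2 (Primary Objectives, Aim 1) sets the goal: "Establish the safety and tolerability of bile acid supplementation". Its method paragraph repeats that "we will establish the safety and tolerability of this intervention". No success criterion is attached.

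Section 7a defines the primary outcome as safety and tolerability: "This will be based on number of adverse events occurring in the two treatment groups and the rate of drop-out in each study arm".

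Section 7c gives the analysis of these components. For AEs: "The incidence rate of AEs will be recorded by system organ class, severity and by relationship to study treatment". For tolerability: "Tolerability analysis will be based on the number (%) of participants who failed to complete the study due to adverse events". Laboratory values get shift tables and summary statistics. The text then turns to quantitative parameters and adds: "We will compare changes over the 16-week treatment period between the groups using mixed effects regression analyses".

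The sample size justification contains the only precision statement for safety. If none of 30 patients has a serious AE, the serious AE rate on TUDCA is taken to be below 5% with 80% confidence. The sample size itself comes from the bile acid outcomes: "with a power of 85% and two-tailed alpha of 0.05 the required sample size would be between 14 – 27 in each arm", and then "Accounting for a 10% drop-out rate, we will aim to recruit 30 participants in each arm of the trial".

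**The concern.** The trial is randomised, blinded and placebo-controlled, yet neither the AE-incidence nor the drop-out component of its primary outcome has a planned between-arm estimate. The plan does not say how two percentages side by side lead to a statement that tolerability has been established.

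This matters because section 8a expects mainly gastrointestinal effects and warns that they may be harder to tolerate for patients with existing bowel problems. Some such events will occur on placebo too, so the quantity of interest is the excess over placebo and how large an excess the data can rule out. With 30 per arm, similar-looking percentages rule out rather little, and a table of n (%) does not show this.

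There is also an ambiguity in the endpoint. Section 7a counts drop-out without naming a cause, while section 7c counts only non-completion due to AEs. A planned contrast has to say which one is primary.

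**Working it through.** **Inputs.** 30 per arm and a 10% drop-out allowance with no cause attached (sample size justification). The serious AE bound: n = 30, zero events, 5%, 80% confidence (same place). No AE-related drop-out rate is given, so the counts in step 3 are assumptions.

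**1. The plan's own figures.**
- Recruitment: 27 / (1 − 0.10) = 30 per arm. Reproduced.
- Serious AE bound with zero events: confidence = 1 − 0.95^30 = 78.5%, against a stated 80%. The exact one-sided 80% upper limit is 1 − 0.2^(1/30) = 5.2%, against a stated 5%. Reproduced to within rounding. The same data at one-sided 95% confidence give 1 − 0.05^(1/30) = 9.5%.

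**2. What each analysis covers.**

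| Element | AE incidence | Drop-out | Compared with placebo? |
|---|---|---|---|
| Tabulation by organ class, severity, relationship (7c) | yes | no | no contrast stated |
| n (%) not completing because of AEs (7c) | no | AE-related only | no contrast stated |
| Mixed model (7c) | no | no | yes, quantitative parameters |
| Serious AE bound (sample size justification) | serious AEs only | no | no, TUDCA arm alone |
| Stopping rules (7d) | individual discontinuation and study holds | no | no |

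The stopping rules govern conduct during the trial and are not an end-of-study criterion.

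**3. Precision of the missing contrast.** The Wilson limits for x events in n, with p = x/n and z = 1.96, are

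(p + z²/2n ± z·√(p(1 − p)/n + z²/4n²)) / (1 + z²/n).

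The Newcombe upper limit for d = p1 − p2 is d + √((u1 − p1)² + (p2 − l2)²), where l and u are the Wilson limits in each arm.

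- 0/30 v 0/30: Wilson limits 0 and 0.1135. Upper limit √(0.1135² + 0²), or 11.4 points.
- 3/30 v 3/30: Wilson limits 0.0346 and 0.2562. Upper limit √(0.1562² + 0.0654²) = 0.169, or 16.9 points.
- 4/30 v 4/30: Wilson limits 0.0531 and 0.2968. Upper limit √(0.1635² + 0.0802²) = 0.182, or 18.2 points.

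Equal counts of 1 and 2 per arm give 13.6 and 15.4 points. Unequal counts shift the interval: 1 v 0 gives +3.3 points (−8.3 to +16.7), and 3 v 0 gives +10.0 (−3.1 to +25.6).

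**4. Sensitivity to method.** For 3 v 3 the half-width is 15.2 points (Wald), 16.2 (Agresti-Caffo), 16.9 (Newcombe) and 17.5 (Miettinen-Nurminen). For 0 v 0, Miettinen-Nurminen gives 11.5; the Wald interval collapses to zero width and should not be used.

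**The case against.** The strongest reply is that this is an early-phase trial sized on metabolomics, that descriptive safety tables are normal in that setting, and that counts from two randomised arms of known size already let any reader work out the difference and its interval. Blinding is justified in section 4c partly by unbiased assessment of adverse effects, so a proper concurrent comparator exists. All of that stands. What is missing is the planned estimate and a rule for reading it, not the data. An early-phase setting is a reason to estimate instead of test, and estimation is what is proposed here.

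Some stronger readings are tempting and should not be drawn:
- *The plan has no bound for safety at all.* It has one, for serious AEs on TUDCA. It is single-arm, at 80% confidence, conditional on zero events, and silent on other AEs and on drop-out.
- *No part of safety is compared with placebo.* Changes in quantitative safety parameters are compared by mixed model. The gap is confined to AE incidence and drop-out.
- *The placebo arm serves only secondary outcomes.* Section 4e lists those uses and does not mention AEs or drop-out, but section 7a collects both by arm.
- *Similar percentages will be declared a success.* No such rule appears. The plan gives no rule either way, and that absence is the point.
- *The trial is too small to test drop-out and should be enlarged.* No such test is planned or needed, so power for one has no bearing here.

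**Conclusion.** The point holds for the AE-incidence and drop-out components of the primary outcome. As planned, the conclusion on safety and tolerability would rest on per-arm counts and percentages, with no estimate of the excess over placebo and no statement of what excess has been excluded.

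For drop-out, equal observed counts of 0 to 4 per arm leave a true excess on TUDCA of about 11 to 18 percentage points within the 95% interval, and a higher upper limit is possible if TUDCA has more events. This range assumes 30 analysed per arm and hypothetical counts. A reader might take about 17 points as the trial's known precision for AE-related drop-out. It is not: it needs 3 of 30 in each arm, and the 10% behind that is a general recruitment allowance, not an AE-related rate.

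This is a worthwhile improvement at low cost. It affects how the primary conclusion is stated, and neither the design nor the data collected need to change.

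**What to change.** In section 7c:
1. Report the TUDCA-minus-placebo risk difference with a 95% CI (Newcombe or Miettinen-Nurminen) for participants with at least one AE, for AE-related non-completion and for all-cause drop-out. A contrast for gastrointestinal AEs is optional.
2. Reconcile sections 7a and 7c by stating which drop-out is the primary measure; keep the other as supporting.
3. State in advance that the safety and tolerability conclusion will be limited to the excess that the upper confidence limit excludes.
4. Keep the serious AE bound, labelled as single-arm and at 80% confidence.

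In Aim 1, replace 'establish' with 'estimate' for the safety and tolerability part. Any precision quoted in advance should be given as the 11 to 18 point range with its assumed counts.

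The cost is a few extra table columns, some rewording and a more modest headline claim. No extra participants, visits or data are needed.
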